3.3 Proposed Intended Use Statement

Allogeneic MSCs are a novel therapeutic option to suppress growth of small AAA. Human MSCs are intended for investigational use only by selected investigators familiar with their use and experienced in conducting clinical studies. Human MSCs may only be administered to human subjects participating in clinical studies sponsored/approved by Indiana University School of Medicine, and who have provided formal written consent.

3.4 Study Objectives.

The principal objective of this study is as follows:

Assess the safety and efficacy of administration of allogeneic MSCs in patients with small AAA.

This study will test the hypothesis that administration of MSCs in doses of 1×10^6 MSCs/kg. and 3×10^6 MSCs/kg demonstrate safety in patients with small AAA. This trial will also test the hypothesis that MSCs, in a dose dependent fashion (1×10^6 MSC/kg. vs. 3.0×10^6 MSC/kg.), promote the frequency and immune suppressor function of Treg cells and decrease AAA inflammation as measured by computed tomography. In an double blinded, Phase I trial, 36 patients with AAA measuring 35-50 mm in maximal transverse diameter (MTD) will be randomized in a 1:1:1 fashion to receive intra-venously either a single dose of 1×10^6 MSCs/kg., 3×10^6 MSCs/kg. , or placebo (Plasmalyte A) (n =12/group). The primary safety endpoints will be incidence of treatment related adverse events accrued over 24 months. Efficacy measures are changes in frequency and immune suppressor function of Tregs, number and cytotoxic activity of CD4+/CD8+ CD28- T-cells, activated monocytes, and changes in aortic inflammation as measured by PET CT compared to baseline. Secondary endpoints measured out to year 5 will include changes in IL-10 and Tr1 levels. Duplex ultrasound measurements of the AAA, which is considered standard of care, will be recorded as change in aortic inflammation during long-term follow-up. Incidence of surgical intervention, aneurysm related death, quality of life, and major adverse cardiac events will be recorded through year five (5).

Completion of this study will determine if MSCs are safe in patients with AAA and provide critical insights that will direct a placebo-controlled, Phase II randomized trial.

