9. STATISTICAL METHODS

The safety of systemic administration of allogeneic MSCs will be measured by treatment-related adverse events. Treatment-related adverse events will be categorized by overlapping systems and severities. The three categories of systems are cardiovascular, respiratory, or infectious. Two categories of severity will be serious adverse (SAE) and major adverse cardiac events (MACE). For completeness, instances of adverse events may appear in more than one category. Within each of these categories adverse events will be listed in descending order of frequency for the treatment-group. In addition, for each category, the sum and difference between the two routes of delivery of the proportions will be reported as percent incidence. Confidence Intervals at the 95% confidence level and *P*-values for these four groups will be calculated. Since four previous trials have not reported adverse events with MSC treatment, confidence intervals will be generated by the method of the Wilson Score Interval because they are robust, with good coverage probability even for small number of trials and are not degenerate near zero. These intervals will be used to summarize the data rather than as any formal inferential statement. No adjustment for multiplicity will be made.

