10. ADVERSE EVENT REPORTING

10.1 Adverse Events and Stopping Rules

Adverse events occurring during the enrollment period should be documented by the Investigator in progress notes, but will not be collected or analyzed by Indiana University School of Medicine unless considered serious by the Investigator. Adverse events will be reported according to federal guidelines for safety reporting for Investigational New Drug Application (IND).

Serious adverse events (SAEs) encountered during study enrollment will be documented by the Investigator and reported to Indiana University School of Medicine immediately upon discovery. SAEs are defined under current Good Clinical Practice (cGCP) guidelines as events that result in one or more of the following:

- life-threatening illness or injury;
- permanent impairment of a body structure or a body function;
- medically necessary in-patient hospitalization;
- medical or surgical intervention necessary to prevent permanent impairment to body structure or function; or
- fetal distress, fetal death, or congenital abnormality.

Serious events that affect the rights, safety, or welfare of subjects must be documented on a form and be reported immediately to Indiana University School of Medicine and to the Investigator’s IRB according to that IRB’s policies.

Major Adverse Cardiac Events (MACE). MACE endpoints will include: death, nonfatal myocardial infarction, including, Q-wave, non Q-wave, and CK/CKMB elevation, stroke, transient ischemic attack (TIA), hospitalization for heart failure, hospitalization for hypo or hypertension, life-threatening arrhythmia, and aneurysm rupture, which will be collected throughout the 6-month time period.

Severity Assessment. We will use the Common Terminology Criteria for Adverse Events (CTCAE), version 4.0, for detailed descriptions of Severity Grades. The CTCAE schema is classified by body system and event using the MedDRA hierarchy and provides descriptions of events that qualify under each severity rating.

The following table contains general descriptions of Adverse Event Severity Grades.

Severity Grade	Description
1	Mild. Asymptomatic or mild symptoms; clinical or diagnostic observations only; intervention is not indicated.
2	Moderate. Minimal, local, or non-invasive intervention indicated or limiting activities of daily living (i.e. preparing meals, shopping for groceries/clothes, managing money, using telephone, etc.)

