11. RISK ANALYSIS

11.1 Potential Risks of the Investigational Product and Clinical Investigation

Study sites will not be provided with an investigational device.

The types of risk associated with injection of allogeneic MSCs align with those associated with injection of autologous bone marrow mononuclear cells (ABMNCs), most notably rash, mild fever, and myalgia. These risks are mild and rare. These risks are all stated in the consent form.

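### The primary safety analysis counts treatment-related adverse events only within three organ systems plus SAE and MACE, so non-serious rash and myalgia, and non-infective fever, enter no category and CTCAE grade is not used

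*Combined protocol and SAP*

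**What the plan says.** Section 3.4 sets the endpoint: "The primary safety endpoints will be incidence of treatment related adverse events accrued over 24 months". The Synopsis gives the same endpoint.

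Section 9 is the only place where its analysis is specified. It says: "Treatment-related adverse events will be categorized by overlapping systems and severities". On systems: "The three categories of systems are cardiovascular, respiratory, or infectious". On severity: "Two categories of severity will be serious adverse (SAE) and major adverse cardiac events (MACE". Events are then ranked by frequency inside each category, and percentages with 95% Wilson score intervals are produced category by category. An event may appear in more than one category. Section 9.2 promises summary safety analyses and describes none.

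Section 10.1 defines SAEs by outcome ("events that result in one or more of the following") and MACE as a list of event types, including stroke and TIA. Severity is handled separately: "We will use the Common Terminology Criteria for Adverse Events (CTCAE), version 4.0, for detailed descriptions of Severity Grades". A table of grades 1 to 5 follows. The same section says that adverse events in the enrollment period go into the investigator's progress notes, but that the sponsor does not gather or analyse them unless the investigator considers them serious.

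Section 11.1 describes the expected risks as "most notably rash, mild fever, and myalgia" and calls them mild and rare. Tables 2 and 3 schedule an AE/SAE evaluation at every visit from baseline to month 60.

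**The concern.** The endpoint covers all treatment-related events, but the analysis covers five categories that do not exhaust them. The wording on systems is closed, with no residual class and no overall row. The allowance for an event to appear more than once deals with overlap and does nothing for an event that fits nowhere.

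The events that fit nowhere include reactions the sponsor itself expects from the product. Section 9 also anticipates few events, because four earlier trials reported none with MSC treatment. A table of zeros would seem to confirm that expectation whether or not mild reactions had occurred.

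The severity label adds a second gap. Neither SAE nor MACE grades intensity, so a shift from grade 1 to grade 2, or to a non-serious grade 3, between 1 and 3 million MSC/kg would not be visible. The trial sets out to test safety at both doses and to direct a Phase II trial, so this matters.

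**Working it through.** The plan states no expected event rate and no precision target for safety, so there is no figure of its own to reproduce. The check has two parts.

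**Which events reach a category.** Applying the section 9 categories and the section 10.1 definitions:

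| Event | Section 9 category |
|---|---|
| Rash or myalgia, non-serious | none |
| Fever, non-serious, not judged infective | none |
| Fever judged infective | infectious |
| Other non-serious, non-MACE event outside the three systems (e.g. hepatic) | none |
| Tachycardia during infusion | cardiovascular |
| Hypoxia, dyspnea | respiratory |
| Stroke, TIA | MACE |
| Any event meeting the SAE definition | SAE |

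The gap is therefore non-serious, non-MACE events outside the three systems.

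**How often that could matter.** Inputs: 12 patients per arm and two MSC arms (section 3.4), so 2 × 12 = 24 treated patients. The rate p of an uncounted related reaction is an assumption. Patients are taken as independent.

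Chance of at least one affected patient = 1 − (1 − p)^24; expected number = 24p.

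| Assumed p | Chance of at least one among 24 | Expected patients |
|---|---|---|
| 1% | 1 − 0.99^24 = 21% | 0.24 |
| 5% | 1 − 0.95^24 = 71% | 1.2 |
| 10% | 1 − 0.90^24 = 92% | 2.4 |

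**What the table would show.** The plan's 95% Wilson interval, with z = 1.96, is

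[x/n + z²/(2n) ± z·√((x/n)(1 − x/n)/n + z²/(4n²))] / (1 + z²/n).

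With x = 0 the upper limit reduces to z²/(n + z²): 3.84/15.84 = 24.2% for n = 12, and 3.84/27.84 = 13.8% for n = 24.

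Suppose, for illustration, that the only related events are non-serious rash or myalgia.

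| Assumed patients affected | Every planned category | Any-related-event row |
|---|---|---|
| 1 of 12 in one arm | 0/12 (0 to 24.2%) | 8.3% (1.5 to 35.4%) |
| 3 of 24 on MSC | 0/24 (0 to 13.8%) | 12.5% (4.3 to 31.0%) |

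**The case against.** The strongest defence is that the five categories are breakdowns. Section 9 opens by measuring safety on treatment-related events without restriction, and section 9.2 promises summary safety analyses, so an overall total is unspecified rather than ruled out. That is fair as far as intent goes. But every listing, percentage and interval in section 9 is defined within a category, and section 9.2 names no table, system or grade. An analyst following the text would not produce the total.

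It can also be said that the label on SAE and MACE changes no count, that system-by-grade tables at 12 per arm will be mostly empty, and that section 9 treats the intervals as descriptive. These points stand. They favour a short summary over a large table, but they do not justify leaving related events out.

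A reader might infer more than the documents support:

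- That every event will be graded and MedDRA-coded, so the data already exist and are simply unused. Section 10.1 adopts CTCAE for describing grades. Its statement "The CTCAE schema is classified by body system and event using the MedDRA hierarchy" describes CTCAE and is not a coding plan. The collection sentence suggests that many non-serious events may never reach the sponsor.
- That none of the three named risks can ever be counted. Infective fever can be, and so can any of them if serious.
- That neurological events as a class are missed. Stroke and TIA are MACE.
- That many patients would go missing from the table. A rate of 10% to 50% would mean 2.4 to 12 of 24, but no rate is given, and the upper part of that range sits badly with risks described as mild and rare.

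**Conclusion.** The point holds for non-serious rash and myalgia, for non-serious fever not judged infective, and for any other non-serious, non-MACE event outside the three systems. Followed as written, section 9 would under-report the stated primary endpoint wherever such events occur, and it would give no picture of severity by dose.

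The size depends on rates the documents do not supply. At assumed true rates of 1% to 10%, the expected number of affected MSC patients is 0.24 to 2.4, and the chance of at least one is 21% to 92%. These figures assume independent patients, and that p is the rate of reactions judged treatment-related that fall in no category. The number of patients is small, but so is the trial, and the endpoint is an incidence. The documents do not show that the product will in fact look safer than it is. They show that the specified analysis could not reveal these events if they occurred.

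The collection sentence in section 10.1 conflicts with the endpoint and with the AE/SAE evaluation at every visit. Unless it is resolved, revising the table alone will not close the gap.

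**What to change.** In section 9, specify for each randomised arm:

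1. The number and percentage of patients with any treatment-related adverse event, with a 95% Wilson interval.
2. An other-systems row, or all body systems, beside the present three, which can stay as events of special interest.
3. A summary by maximum CTCAE grade per patient.
4. SAE as a seriousness row and MACE as an event-type row, no longer called severity.

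In section 10.1, define the enrollment period and reconcile the sentence on uncollected non-serious events with the 24-month endpoint and with Tables 2 and 3. State that non-serious events are recorded, assessed for relatedness and graded. For patients already treated, the progress notes that section 10.1 requires are the natural source from which to recover these events.

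The cost is modest but goes beyond extra table rows, because it includes recording, grading and classification work for non-serious events. Cells will be sparse at 12 per arm, so the any-event row and a short grade summary should carry the message, with finer breakdowns given as listings. No change to sample size, visits or randomisation is needed.

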7. STUDY PROCEDURES

7.1 Workflow

MSC preparation. Donor infectious disease testing will be performed by CLIA certified Laboratories. Allogeneic donor Infectious Diseases testing will include anti-HIV-1/2 and anti-HCV. Testing will be repeated if it exceeds 30 days. Potential donors whose testing is incomplete or not available within 30 days will not be eligible to donate bone marrow and testing will be repeated to confirm ID markers. Potential donors testing positive for any of these infectious diseases will NOT be eligible.

Randomization Scheme and MSC Dosing. The PI, [name] MD., will determine inclusion in the study. After that decision has been rendered, the patient will be screened for enrollment. After enrollment, 36 patients will be randomized to receive MSCs or placebo IV through an antecubital vein (**Figure 1**).

Serum samples will be collected pre-MSD administration, 1 and 6 months' post MSC-treatment and analyzed in the Cellular Therapy Laboratory of University Hospital to determine if patients develop antibodies against allogeneic MSCs.

Baseline Screening and Follow-Up Schedule. The following evaluations will be carried out at baseline to determine if patient is eligible for study: (1) Baseline blood tests (complete blood count, serum chemistries and liver panel); (2) infectious disease panel and HLA typing; (3) medical history and physical exam; (4) concomitant medications; (5) pregnancy test for women of childbearing age ;(6)12 lead ECG; (7) 18-fluorodeoxyglucose (FDG) uptake with positron emission tomography/computed tomography (PET/CT) will be performed at baseline and Day 14. Computed tomographic angiography of the abdominal aorta and iliac arteries (as part of "Standard of Care") will be performed at month 12. Duplex ultrasound of the aorta will be performed at month 12 while the patients are enrolled in the trial to monitor AAA size. Follow up studies are detailed in **Table 2**, below. Subjects will return for long-term follow-up visits at six month intervals from year 1 (+/- 4 weeks) through year 5 (+/- 4 weeks). Window ranges for follow-up visits are guidelines for scheduling and will not be considered a protocol deviation if visits fall outside of these ranges. See **Table 3**, below, for details on the long-term follow-up visits.

- Annual CT abdominal exams beginning at year 1 are considered Standard of Care.

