Primary attention in Aim 1 will focus on the detection of cellular immunosuppression activity coincident with MSC administration in both proliferation (six decreasing and one increasing) and function (three decreasing functional outcomes). Ten mixed model repeated measures with a fixed term for MSC dose and their appropriate baseline covariate will be fit. The denominator degrees of freedom will be estimated by the method of Kenward and Rodger.¹² A compound symmetry covariance structure will be fit if the model with the unstructured covariance does not converge. For these data the directionality of superiority or inferiority will be assessed. Specifically, the alternative hypotheses are that (1) three T-cell counts (CD4⁺CD28⁻, CD8⁺CD28⁻ T-cells and Th-17⁺ T-cell) will be decreased; (2) CD28⁻ T-cell function will be inhibited (decreased; as measured by IFN- γ -producing cells, Perforin-producing cells, and CD57 expression); (3) T-regulatory cells (CD4⁺Fox3P⁺ T-regs) will be increased; and (4) monocytes will be decreased (fewer CD45⁺CD14⁺⁺CD16⁻, CD45⁺CD14⁺CD16⁺, CD45⁺CD14dim/CD16⁺⁺). To assess the individual hypotheses, the model-derived, confidence interval for the intercept will be reported. Confidence intervals at the 95% level from the same models will be constructed to estimate the difference, or contrast, between routes of administration

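### Section 9 contrasts routes in a one-route, three-arm trial, names no comparison with placebo or between doses, and judges efficacy on a model intercept

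*Combined protocol and SAP*

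**What the plan says.** The design is the same throughout the protocol. The Synopsis, 3.4 (Study Objectives) and 6.1.4 describe 1:1:1 randomisation to 1 million MSC/kg, 3 million MSC/kg or Plasmalyte A, 12 in each arm. Section 7.1 gives a single route: "36 patients will be randomized to receive MSCs or placebo IV through an antecubital vein". The efficacy aim is also about arms. Section 2 sets out to compare the two doses, and 3.4 states: "This trial will also test the hypothesis that MSCs, in a dose dependent fashion".

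Section 9 describes a different comparison.

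- **Safety:** "the sum and difference between the two routes of delivery of the proportions will be reported as percent incidence". Confidence intervals and P-"values for these four groups will be calculated". The Wilson score interval is named, with the proviso that "These intervals will be used to summarize the data rather than as any formal inferential statement".
- **Efficacy (Aim 1), model:** "Ten mixed model repeated measures with a fixed term for MSC dose" and a baseline covariate.
- **Efficacy, hypotheses:** the plan lists ten directional alternatives, then says "To assess the individual hypotheses, the model-derived, confidence interval for the intercept will be reported".
- **Efficacy, contrast:** 95% intervals from the same models are built "to estimate the difference, or contrast, between routes of administration".

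Sections 9.1 and 9.2 name no contrast.

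**The concern.** There are two separate faults.

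1. **The named contrasts do not exist in this trial.** With one route there is nothing to contrast by route. The comparisons that the design supports (each dose with placebo, and one dose with the other) appear nowhere in section 9. Someone would have to choose them later, possibly with data in hand.
2. **The intercept does not use the randomised control as a control.** Replacing routes by doses would leave this untouched. What the intercept estimates depends on the coding of the dose term, the centring of the baseline and whether the outcome is a level or a change, and section 9 states none of these.

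The risk is that a movement shared by all arms (assay drift, disease course, or the premedication that 6.1.4 describes without separating arms) is credited to MSCs, or that a real MSC effect is missed. Section 3.4 expects the results to direct a Phase II trial.

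**Working it through.** **Counts.** 3 arms × 12 = 36, which agrees with the stated total. The ten models agree with the listed outcomes: 6 decreasing + 1 increasing proliferation outcomes + 3 functional outcomes = 10. One route gives 0 possible route pairs; three arms give 3 arm pairs, none of them named in section 9.

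**If routes is read as doses.** Placebo is still left out. With equal arms, the literal sum of two proportions is x₁/12 + x₂/12 = 2 × (x₁ + x₂)/24, twice the pooled incidence. With assumed counts 2/12 and 3/12, the sum is 41.7%, against pooled 5/24 = 20.8% (Wilson 95% interval 9.2% to 40.5%).

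**What the intercept estimates.** Take change from baseline with centred baseline, a shift s common to all arms, and MSC effects d₁ and d₃ in the 1 and 3 million/kg arms:

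| Coding | Intercept estimates | Standard error (residual SD 1) |
|---|---|---|
| Placebo as reference | s | 1/√12 = 0.289 |
| 3 million/kg as reference | s + d₃ | 1/√12 = 0.289 |
| Sum to zero | s + (d₁ + d₃)/3 | 1/√36 = 0.167 |

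The contrast 3 million/kg minus placebo estimates d₃, and pooled MSC minus placebo estimates (d₁ + d₃)/2. Neither contains s.

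**How often the 95% interval excludes zero.** Only the 12 per arm comes from the documents; everything else is assumed. Single-visit analysis of covariance, 36 − 4 = 32 residual df, t = 2.037, 20,000 simulated trials per setting.

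| Setting (SD units) | Intercept, placebo reference | Intercept, sum coding | Arm contrasts |
|---|---|---|---|
| No effect, shift 0.25 | 14% | 31% | about 5% |
| No effect, shift 0.5 | 39% | 83% | about 5% |
| No effect, shift 1 | 91% | over 99% | about 5% |
| Effect 1 in both MSC arms, no shift | 5% | 97% | 3 million/kg − placebo 65%; pooled MSC − placebo 77% |
| Same effect, shift −0.67 | not tabulated | 5% | pooled MSC − placebo 77% |

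- In the fourth setting, an intercept with 3 million/kg as reference excludes zero in 91%. One data set can therefore give 5%, 91% or 97% according to a coding choice that the plan leaves open.
- The last setting is chosen so that s + (1 + 1)/3 = 0. It shows that a real effect can be cancelled out of the sum-coded intercept.
- Noncentral-t check: for shift 0.5, noncentrality 0.5/0.289 = 1.73 gives 39.0% and 0.5/0.167 = 3.0 gives 82.9%. For an effect of 1, 3 million/kg minus placebo (SE √(2/12) = 0.408) gives 66% and pooled MSC minus placebo (SE √(1/24 + 1/12) = 0.354) gives 78%, ignoring the small loss from fitting the baseline.
- Repeated-measures check: mean of three visits, compound symmetry, within-patient correlation 0.8 / 0.5 / 0.3, no effect, shift 0.5. The placebo-reference intercept excludes zero in 43% / 54% / 63% and the sum-coded intercept in 88% / 94% / 98%; 3 million/kg minus placebo stays at about 5%.

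**What the safety contrasts would look like.** The Wilson interval covers one proportion. Newcombe's method combines two Wilson intervals into one for a difference. With assumed counts:

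| Difference | Estimate (points) | 95% interval (points) |
|---|---|---|
| Pooled MSC 0/24 − placebo 0/12 | 0 | −24.2 to 13.8 |
| Pooled MSC 5/24 − placebo 0/12 | 20.8 | −6.0 to 40.5 |
| 3 million/kg 3/12 − 1 million/kg 2/12 | 8.3 | −24.1 to 39.0 |

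**The case against.** The best defence is that this is loose wording in a small exploratory study. Routes may be a slip for doses, the model contains a dose term, and sections 2 and 3.4 make the dose comparison plain. The intercept may be meant as average change from baseline, since 3.4 describes the efficacy measures as changes compared to baseline; the plan never calls it a between-arm contrast. The safety intervals are expressly descriptive, efficacy is exploratory in the Synopsis, 9.2 promises summary analyses, and halting follows separate rules in 10.1.

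Several points stand. The four groups may be two groups plus their sum and difference, so that phrase is only supporting evidence. The word sum may have been meant as pooled incidence. The confidence level of the intercept interval is not stated; 95% is assumed here. Seven post-infusion blood samples are scheduled to month 24, but the notes to the schedule label these draws as being for ancillary studies, and the month 30 to 60 samples are not shown to feed the ten models. The percentages above are illustrative.

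The core is unaffected. Reading routes as doses still omits placebo. Reading the intercept as average change still cannot attribute that change to MSCs when a randomised control is available. A descriptive estimate still needs a defined comparison.

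**Conclusion.** The concern holds. As written, section 9 contains no between-arm comparison that can be computed, for safety or for efficacy, and it rests ten directional hypotheses on a quantity that does not isolate an MSC effect. This is wrong as written, not merely missing detail, and should be corrected before any analysis.

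It weighs most on efficacy. Under the stated assumptions, a modest common shift of 0.5 SD makes the intercept point to a change in 39% to 83% of trials with no MSC effect. With a 1 SD effect and no shift, the placebo-reference intercept detects nothing beyond the nominal 5%. The safety part is less serious because those intervals are descriptive. The damage is to what is estimated and reported, not to a confirmatory error rate. The direction of these results follows from the algebra of the intercept; the exact percentages depend on the assumed SD, shift, effects and single visit.

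**What to change.** **Safety paragraph of section 9.** Replace the route wording, the sum and the four groups with a named list:

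- Incidence with Wilson interval for each arm and for pooled MSC (patients with events over all patients in both dose arms).
- Differences for each dose minus placebo, pooled MSC minus placebo, and 3 minus 1 million/kg, with a named interval method for a difference. Newcombe's is the natural companion to the Wilson interval already chosen.
- Which comparisons the P-values refer to, and the test used.

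Keep the statement that these intervals are descriptive.

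**Efficacy paragraph.** Replace the intercept interval and the route contrast with the same contrasts of adjusted means, from a categorical dose term that includes placebo, at a visit named in advance. Add visit and dose-by-visit terms; the covariance fallback already planned can remain for non-convergence. State whether the outcome is the level or the change, and keep the direction already listed for each marker.

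The pooled contrast and Newcombe's method are sensible choices, not requirements of the documents. What is essential is that the arm contrasts are named, include placebo, and are fixed before the data are seen.

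**Cost.** Section 9 wording only: no new data, visits or patients.

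### Section 9 reports a sum and a difference of proportions between two routes that this IV-only, three-arm trial does not have; a sum is not an incidence, and no valid interval is specified for a difference

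*Combined protocol and SAP*

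**What the plan says.** The first paragraph of section 9 sorts treatment-related adverse events into three body systems and two severities. For each category, "the sum and difference between the two routes of delivery of the proportions will be reported as percent incidence". It then plans "Confidence Intervals at the 95% confidence level" and P-values "for these four groups will be calculated". The groups are not defined and no test is named. On method it says only that "confidence intervals will be generated by the method of the Wilson Score Interval". On use it says "These intervals will be used to summarize the data rather than as any formal inferential statement", and on multiplicity "No adjustment for multiplicity will be made".

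The second paragraph of section 9, on the cellular outcomes, also ends with a contrast between routes of administration.

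The design is different. Section 3.4 (Study Objectives) and the Synopsis describe three arms, two MSC doses and placebo, with 12 patients each. Section 7.1 (Workflow) says "36 patients will be randomized to receive MSCs or placebo IV through an antecubital vein", so there is one route. Section 3.4 makes the incidence of treatment-related adverse events over 24 months the primary safety endpoint.

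**The concern.** An analyst cannot carry out this paragraph as it stands.

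- **Comparison.** There are no two routes, so the two proportions to be summed and differenced are not identified. They could be the two doses, or MSC and placebo, and the result means something different in each case.
- **Sum.** Two proportions added together are not the incidence in anyone. An incidence in the combined patients is total events over total patients.
- **Difference.** The Wilson interval is an interval for a single binomial proportion. The plan does not say how to get from it to an interval for a difference.
- **Four groups.** Nothing listed comes to four: there are three arms and five adverse-event categories (3 + 2). Three arms plus a pooled MSC group would make four, as would two proportions with their sum and difference. The text states neither.

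At stake is the headline safety table. Section 9 states no other estimator or interval for the primary safety endpoint, and section 3.4 says that the completed study will settle whether MSCs are safe and direct a Phase II trial.

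**Working it through.** The documents give no expected event rate, interval value or precision target for safety, so there is no figure of the plan's own to reproduce.

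**Inputs.** Arm size 12 (Synopsis, section 3.4). Confidence level 95% (section 9), taken as two-sided, z = 1.96. Event counts are illustrative. I assume 12 evaluable patients per arm, each counted once per category.

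**Sum.** For two arms of 12, x1/12 + x2/12 = 2 × (x1 + x2)/24, exactly twice the pooled incidence.
- 3/12 and 1/12: the sum is 4/12 = 33.3%; the pooled incidence is 4/24 = 16.7%, Wilson 6.7 to 35.9.
- 7/12 and 6/12: the sum is 13/12 = 108.3%. Of the 13 × 13 = 169 possible count pairs, 78 give a sum above 100%.
- With unequal groups the factor is not exactly two. Pooled MSC 4/24 plus placebo 1/12 gives 16.7 + 8.3 = 25.0%, against 5/36 = 13.9% in all patients. The sum is still not an incidence.

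**Difference, if the one-sample formula were put on it.** The Wilson limits for a proportion p with n patients are

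[p + z²/2n ± z√(p(1−p)/n + z²/4n²)] / (1 + z²/n).

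The lower limit is above zero when (p + z²/2n)² exceeds z²p(1−p)/n + z⁴/4n². The left side minus the right is p²(1 + z²/n), which is positive for every p above 0. A positive difference entered as p therefore always gets an interval that excludes zero.

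For p = −1/12 and n = 12, the term under the root is −(1/12)(13/12)/12 + 3.8416/576 = −0.00752 + 0.00667, which is negative, so no limits exist. Over all count pairs, the lower limit is above zero in 78 of the 78 with a positive difference, and there are no limits in 78 of the 78 with a negative one.

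**Difference by a two-sample form.** The Newcombe hybrid-score interval uses the Wilson limits (l, u) of each arm. With d = p1 − p2,

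lower = d − √[(p1 − l1)² + (u2 − p2)²], upper = d + √[(u1 − p1)² + (p2 − l2)²].

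For 1/12 against 0/12, the Wilson limits are (0.0149, 0.3539) and (0, 0.2425):
- lower = 0.0833 − √(0.0684² + 0.2425²) = 0.0833 − 0.2520 = −0.169
- upper = 0.0833 + √(0.2706² + 0²) = 0.354

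| Counts | Difference (points) | One-sample Wilson, n = 12 | Newcombe |
|---|---|---|---|
| 1/12 vs 0/12 | 8.3 | 1.5 to 35.4 | −16.9 to 35.4 |
| 3/12 vs 1/12 | 16.7 | 4.7 to 44.8 | −14.8 to 45.7 |
| 1/12 vs 3/12 | −16.7 | none | −45.7 to 14.8 |

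Of the 78 pairs with a positive difference, Newcombe covers zero in 40.

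**The case against.** The strongest reply is that the paragraph is loosely worded and not wrong in intent. A sum to be reported as an incidence may simply mean the incidence in the combined groups. The plan never says that one-sample Wilson limits go on a sum or a difference. Wilson limits are also the building blocks of the Newcombe interval, so the method named is compatible with a valid analysis. The intervals are declared descriptive, section 9.2 promises only summary analyses, and the stopping rules in section 10 are worded as event counts and do not use these intervals.

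Much of this stands. A reader might infer that the plan's difference intervals can never cover zero. That follows only if the four groups include the difference and the one-sample formula is applied to it, and the text states neither. What the documents support is that the interval for a difference is unspecified. A reader might also infer a false-positive problem. Under that same reading, with assumed equal true rates of 5%, 10% or 20% in two arms of 12, the first arm is higher by chance in 29%, 36% or 40% of trials. The documents attach no decision to such a result, and they give no rates. Sums above 100% need more events than a plan expecting counts near zero has in mind. Finally, the remark that instances of an event may appear in several categories describes cross-classification between overlapping categories; it does not say that a patient counts twice within one. Only the denominator is unstated.

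The defence does not rescue the sentence. It asks for the sum of the proportions, and that is wrong if followed. A descriptive rate that is doubled is still a wrong rate. P-values are planned with no test named. No reading supplies the second route.

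**Conclusion.** Wrong as written, in a limited sense. Three things are firm: the comparison named does not exist in this trial; a literal sum of two arm proportions is not an incidence, and with 12 per arm it is exactly double the pooled rate; and no interval is specified for a difference, nor any test for the P-values. The doubling assumes the literal wording and two arms of equal size. The one-sample intervals in the table assume a reading that the plan does not commit to, so they show why the method must be named and are not a forecast of what will be reported. No decision rule in the documents is affected. It should still be corrected before analysis, because the paragraph governs the primary safety endpoint.

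**What to change.** Replace the sentence in section 9 with the following:

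- **Incidence:** for each category, patients with at least one event divided by patients, in each of the three arms and in the two MSC arms pooled (denominator 24), each with a 95% Wilson interval.
- **Differences:** each dose minus placebo and pooled MSC minus placebo, and if wanted high minus low dose, with 95% Newcombe hybrid-score intervals.
- **Unit:** the patient, counted once per category; a patient may still appear in several categories.
- **P-values:** name an exact test for the listed differences, or drop them. Dropping them fits the stated descriptive purpose.
- **Deletions:** the sum, the two routes and the four groups. Replace the contrast between routes at the end of the second paragraph with a named dose or placebo contrast.

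The cost is a few sentences and no new data. Difference intervals will be wider than under the literal one-sample reading: for 1/12 against 0/12 the width goes from 35.4 − 1.5 = 33.9 points to 35.4 + 16.9 = 52.3 points, which is what 12 patients per arm can support.
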